5.3 Pharmacokinetics Assessment

Plasma PK assessments will be performed as follows for all subjects at all sites:

Baseline, Weeks 4 and 8

PK draws will be collected while the subject is having serum chemistries drawn. At Baseline, the draws will be pre-dose drug application in the clinic. Ensure the IP is not applied in the area where PK will be drawn.

5.4 Final Study Visit

The approximate final study visit will occur at Week 9. The procedures performed during these visits are described in the Schedule of Visits and Assessments (Section 1.3). A 5-day scheduling window is allowed for this visit. Adverse events will be recorded as reported by the participant or followed to resolution as outlined in Section 5.1.10.

5.5 Early Termination Visit

If a subject is withdrawn or wishes to exit the study, a termination visit will be scheduled. This visit should include the procedures and assessments that would be performed at the Week 9 visit (Day 63).

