1.3 Schedule of Visits and Assessments

Study Procedure	Screen	Baseline Day 0	Wk 2 Day 14	Wk 4 Day 28	Wk 8 Day 56	Wk 9 Day 63
Visit	1	2	3	4	5	6
Visit Window	-4 weeks		+/- 3 day	+/- 5 days	+/- 5 days	+/-5 days
Informed consent/assent	Х					
Medical history	Х					
Physical examination ^a	Х	Х			Х	
I/E criteria	Х	Х				
Randomization		Х				
Hematology, Serum Chemistries, and Urine Analysis	Х	Х			Х	
Vital signs, height, weight ^b	Х	Х	X	Х	Х	Х
IGA ^c , Overall Assessment of Erythema ^c , Overall Assessment of Scaling ^c	Х	Х	Х	Х	Х	Х
WI-NRS, DLQI, Scalpdex	Х	Х	Х	Х	Х	
BSA	Х	Х			Х	
Application Site Reaction Assessment/Local Tolerability ^d		Х		Х	Х	
Pigmentation Assessment ^e	Х	Х	Х	Х	Х	Х
C-SSRS, PHQ-8	Х	Х		Х	Х	
Medical Photography ^f		Х	Х	Х	Х	
Pregnancy test ^g	Х	Х		Х	Х	
PK draws ^h		Х		Х	Х	
IP/vehicle application at the study site ⁱ		Х	Х			
Dispense study medication kit ^j		Х	X	Х		
Dispense/review diary		Х	X	Х	Х	
Weigh study medication kit ^k		Х	X	Х	Х	
Compliance calculation ¹		Х	Х	Х	Х	
Adverse event assessment	Х	Х	Х	Х	Х	Х
Concomitant medications	Х	Х	Х	Х	Х	Х

Footnotes:

^a Limited physical examination: skin, lungs, and heart only

- ^b Height will be collected at Baseline and Week 8. Weight will be collected at all study visits. Subject to void prior to weight being taken. Remove any jackets, outerwear and shoes. Remove any objects of significant weight (i.e. cell phones, wallet, key chains). A 5% weight loss from Baseline should be reported to the medical monitor.
- ^c IGA will be a 5-point scale ranging from clear (0) to severe (4). IGA should be completed prior to other physician assessments. Overall assessment of erythema (0-3 scale) and overall assessment of scaling (0-3 scale) will be completed.
- ^d Local tolerability Assessments: The Investigator local tolerability assessment of skin irritation (Berger and Bowman skin irritation score) should be performed prior to the investigational product application at Baseline, and at Weeks 4 and 8. Reactions at the site of product application, which may occur post-Baseline, should be differentiated from the preexisting inflammation associated with the subject's seborrheic dermatitis. Subjects will perform the local tolerability assessment 10-15 minutes post-drug application at Baseline, and recall assessments at Weeks 4 and 8 for the subject's '0-3' burning/stinging assessment.

Protocol ARQ-154-203 Amendment 1

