- ^e An assessment for hypopigmentation and hyperpigmentation will be performed by the Investigator at all clinic visits.
- ^f At selected sites, medical photography will be obtained for target lesions. All efforts will be made to de-identify the subjects. Subjects who are unwilling to participate in the medical photography will be allowed to opt out of this procedure.
- ^g A pregnancy test will be administered to all females of child-bearing potential. A serum pregnancy test will be performed at the Screening visit only. A urine pregnancy test will be performed at Baseline, Week 4, and Week 8. A negative result is required for continued participation in the study, and results must be available prior to dispensing of investigational product at each visit.
- ^h PK draws (trough / pre-dose) will be collected at Days 0, 28 and 56. At baseline, this draw will be pre-dose relative to drug application in the clinic. Ensure study medication is not applied in the area where PK will be drawn.
- ⁱ Subjects to apply assigned IP at the study site at every designated visit, to confirm understanding of instruction on how to apply initially.
- ^j Kits will be dispensed based on %BSA affected. See IP Handling Manual for details.
- ^k The entire kit should be weighed and recorded at every visit. See IP Handling Manual for details.
- ¹ Compliance calculation is described in the IP Handling Manual

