5.1.3 Physical Examination

Physical examinations will be performed as follows:

Screening, Baseline and Week 8.

The physical exam will be limited to skin, lungs and heart only.

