5.1.6 Patient Health Questionnaire depression scale (PHQ-8)

The 8 item PHQ-8 Assessment (see Appendix 1) will be completed by the subject at the following visits:

Screening, Baseline, Week 4, and Week 8

A subject with a PHQ-8 score of '15' or above should be referred promptly to a mental health care professional and, if currently applying investigational product, consideration should be given to discontinuation from investigational product.

Subjects with PHQ-8 \geq 10 at Screening or Baseline will be excluded from the study.

PHQ-8 score is the sum of the responses for the 8 questions.

Five severity categories of depression are defined as follows:

- None Minimal depression (0 to 4)
- Mild depression (5 to 9)
- Moderate depression (10 to 14)
- Moderately severe depression (15 to 19)
- Severe depression (20 to 24)

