5.1.8 Local Tolerability Assessments

The Investigator Local Tolerability Assessment will be an overall assessment of local tolerability and performed as follows:

Baseline, Weeks 4 and 8

Application site reactions will be graded at the timepoints outlined in the Schedule of Visits and Assessments (Section 1.3). Irritation reactions are graded using the scale detailed in the following section (Berger 1982). Reactions at the site of product application, which may occur post-Baseline, should be differentiated from the preexisting inflammation associated with the subject's seborrheic dermatitis.

The Investigator assessments will be conducted by the Investigator prior to any investigational product application in the study site.

Dermal Response

- 0 = no evidence of irritation
- 1 = minimal erythema, barely perceptible
- 2 = definite erythema, readily visible; minimal edema or minimal papular response
- 3 = erythema and papules
- 4 = definite edema
- 5 = erythema, edema and papules
- 6 = vesicular eruption
- 7 = strong reaction spreading beyond application site

Other Effects

- A = slight glazed appearance
- B = marked glazing
- C = glazing with peeling and cracking
- D =glazing with fissures
- E = film of dried serous exudates
- F = small petechial erosions and/or scabs
- G = no other effects

The Subject Local Tolerability Assessment will be an overall assessment of local tolerability and performed as follows:

Baseline, Weeks 4 and 8

This assessment will be administered at Baseline by the site 10 to 15 minutes after IP application at the study site. Assessments at the study site during Weeks 4 and 8 will be a recall assessment of the subject's experience 10-15 minutes after IP application since the last study visit.

Grade	Sensation Following Investigational Product Application
0 (none)	No sensation
1 (mild)	Slight warm, tingling sensation; not really bothersome
2 (moderate)	Definite warm, tingling sensation that is somewhat
	bothersome
3 (severe)	Hot, tingling/stinging sensation that has caused definite
	discomfort

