5.2.4 Body Surface Area (BSA)

BSA Assessments will be performed as follows:

Screening, Baseline, and Week 8

The BSA affected by seborrheic dermatitis will be determined by the subject's hand method, where the subject's hand (including fingers) surface area is assumed to equal 1% of body surface area (BSA).

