5.2.5 Worst Itch Numerical Rating Scale (WI-NRS)

Given that itch is an important symptom of seborrheic dermatitis, a WI-NRS assessment is included in the present study. A responder analysis will be performed to evaluate achievement of a 4-point reduction of WI-NRS, which has been described as optimal for demonstrating a level of clinically meaningful improvement in itch severity in other skin conditions, including other forms of eczema (Yosipovitch 2019) and psoriasis (Kimball 2016).

WI-NRS Assessments will be performed as follows:

Screening, Baseline, Weeks 2, 4, and 8

The WI-NRS has been developed as a simple, single item to assess the patient-reported severity of this symptom at its highest intensity during the previous 24-hour period. (Naegeli 2015). The WI-NRS will be determined by asking the subject's assessment of worst itch over the past 24 hours. The scale is from '0 to 10' ("no itch" to "worst imaginable itch"). Subjects will complete the WI-NRS pruritus assessment.

No itch

Worst imaginable itch

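### The early termination visit copies the Week 9 list, so subjects who leave before Week 8 have no scheduled post-baseline labs or physical examination, and those who leave before Week 4 have no PHQ-8, C-SSRS, local tolerability or pregnancy test after the Baseline visit

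*Protocol*

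**What the plan says.** Section 5.5 provides a termination visit for any subject who is withdrawn or wishes to leave the study, and fixes its content: "This visit should include the procedures and assessments that would be performed at the Week 9 visit (Day 63"). It does not distinguish exits by timing, and the schedule in Section 1.3 has no early termination column.

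The other sections set these times:

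- The schedule row "Hematology, Serum Chemistries, and Urine Analysis" is marked at Screening, Baseline and Week 8 only. Section 5.1.5 refers to the schedule for timing.
- Physical examination (5.1.3): "Screening, Baseline and Week 8".
- BSA (5.2.4): "Screening, Baseline, and Week 8".
- PHQ-8 (5.1.6): "Screening, Baseline, Week 4, and Week 8". Section 5.1.7 gives the same visits for the C-SSRS.
- Local tolerability, Investigator and subject (5.1.8): "Baseline, Weeks 4 and 8".
- Pregnancy (1.3, footnote g): "A urine pregnancy test will be performed at Baseline, Week 4, and Week 8". The serum test is at Screening only.
- WI-NRS (5.2.5), with DLQI and Scalpdex on the same row: "Screening, Baseline, Weeks 2, 4, and 8".

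None of these items is marked at Week 9. What Week 9 does contain is vital signs with weight; IGA with the erythema and scaling assessments; pigmentation; adverse events; and concomitant medications.

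**The concern.** Week 9 falls one week after the last dose (4.3). Its short list suits a subject who had the full Week 8 work-up a few days before. It does not suit someone who leaves at, say, Week 3 and never had that work-up.

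Section 5.1 names physical examination, local tolerability, laboratory parameters, PHQ-8 and C-SSRS among the assessments by which safety is determined. Section 6.4.6 plans a laboratory shift table and Section 6.4.4 a shift in PHQ-8 category; a shift needs a post-baseline value. The protocol describes this as the first study of the foam (3.1), and it reports psychiatric events on oral roflumilast at 5.9% against 3.3% on placebo (3.3.2). If tolerability or mood contributes to leaving, the missing values fall among the subjects whose safety data may be most informative. A statistical analysis plan can assign or impute values, but it cannot collect them, so visit content has to be settled in the protocol.

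**Working it through.** **Step 1. Count the schedule rows (Section 1.3).** Week 8 has 17 marked rows and Week 9 has 5, all of them also marked at Week 8. Rows not taken at an early exit: 17 - 5 = 12. They divide as follows:

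- 5 safety rows: labs; physical examination; C-SSRS/PHQ-8; local tolerability; pregnancy test.
- 2 rows of efficacy or patient-reported measures: BSA; WI-NRS/DLQI/Scalpdex.
- 5 other rows: PK; photography; diary; kit weighing; compliance.

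5 + 2 + 5 = 12.

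**Step 2. Apply Section 5.5 by time of exit.** The table gives the number of scheduled assessments after the Baseline visit, assuming the subject attended every visit before leaving and then the termination visit.

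| Assessment | Scheduled after Baseline | Leaves before Week 4 | Leaves between Weeks 4 and 8 | Completes Week 8 |
|---|---|---|---|---|
| Labs | Week 8 | 0 | 0 | 1 |
| Physical examination | Week 8 | 0 | 0 | 1 |
| BSA | Week 8 | 0 | 0 | 1 |
| PHQ-8 | Weeks 4, 8 | 0 | 1 | 2 |
| C-SSRS | Weeks 4, 8 | 0 | 1 | 2 |
| Local tolerability | Weeks 4, 8 | 0 | 1 | 2 |
| Urine pregnancy test, where applicable | Weeks 4, 8 | 0 | 1 | 2 |
| WI-NRS, DLQI, Scalpdex | Weeks 2, 4, 8 | 0 or 1 | 2 | 3 |

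On local tolerability, the zero refers to the time after the Baseline visit. The subject's own score taken 10 to 15 minutes after the first application at Baseline (5.1.8) does exist.

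**Step 3. Look for a provision elsewhere that restores these items.**

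- Section 5.1 lets the Investigator and/or the Sponsor call for additional testing. Sections 5.1.5 and 5.6 allow unscheduled laboratory tests and visits on the Investigator's judgment. All of this is permitted; none is required.
- Sections 5.1.10 and 5.7.4 follow adverse events and clinically significant laboratory values for up to one month after the end of treatment. Section 5.9 calls for contact with the Medical Monitor and for mental health referral in defined situations. These act on a finding already made. A PHQ-8 score that was not taken cannot trigger the referral in Section 5.9.

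No section requires an exit laboratory test, examination or questionnaire.

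**Step 4. Size of the group.** The Synopsis assumes that 159 of 184 subjects complete. 159/184 = 86.4%, which agrees with the stated 86%. Planned non-completers: 184 - 159 = 25, and 25/184 = 13.6%. The protocol gives no distribution of exit times, so within these 25 the number leaving before Week 4 could be anything from 0 to 25.

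**The case against.** The case against changing anything has several parts.

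*Safeguards exist.* Extra testing can be ordered by the Investigator or the Sponsor, and adverse events and significant findings are followed after exit. This stands, and it narrows the gap. But testing on judgment is selective, and it will not give uniform exit data for a shift table.

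*The subjects of most safety interest may not be affected.* Section 4.4.3 lists adverse events, weight loss, PHQ-8 or C-SSRS findings and pregnancy as reasons to stop the investigational product. Section 4.4.4 lists only withdrawal by the subject, loss to follow-up and study termination as reasons to leave the study. Subjects who stop the product may thus remain on the Week 4 and Week 8 schedule, though the protocol does not say so outright. Subjects lost to follow-up attend no termination visit, so a fuller visit cannot help them. Both points stand and reduce the number who would benefit.

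*Some rows carry little weight.* The physical examination covers only skin, lungs and heart, and its clinically significant changes are reported as adverse events (6.4.3), which are collected at exit. The pregnancy test is tied to continued participation and to dispensing, and Section 6 plans no analysis of it. The BSA endpoint is fixed at Week 8 and the patient-reported endpoints at Weeks 2, 4 and 8, so an off-schedule exit value is not the endpoint; multiple imputation is already planned for continuous secondary endpoints. This stands for BSA and the patient-reported measures, which is why they are optional in the fix. It weakens but does not remove the case for the examination and the pregnancy test, and it does not touch labs, PHQ-8 or C-SSRS.

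*The safety summaries are descriptive and no stated figure is wrong.* True, and this limits the severity.

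**Conclusion.** The point holds as a weak design choice that should be corrected. Under Section 5.5 as written, a subject who leaves before Week 8 contributes no scheduled post-baseline value to the laboratory shift table, and one who leaves before Week 4 contributes none to the PHQ-8 shift or the C-SSRS summary. The main loss is in labs, PHQ-8 and C-SSRS.

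Four stronger readings are tempting, and the protocol does not support them:

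- A reader might infer that Section 5.5 contradicts the schedule. It does not; the two are consistent, and the list chosen is simply too short for early exits.
- A reader might infer that the primary measure is lost. IGA, erythema, scaling, vital signs, weight, pigmentation and adverse events are all taken at exit.
- A reader might take 25 subjects as the most that could be affected. It is the number of non-completers implied by a sample size assumption. Actual exits could exceed it, and the number affected could be smaller if some leave after Week 8, are lost to follow-up, or stop only the product.
- A reader might infer that early leavers have no tolerability data. The subject's score after the first application at Baseline is available.

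The conclusion rests on the schedule marks, which agree with the procedure sections, and on Section 5.5 being followed as written.

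**What to change.** Amend Section 5.5, and add a matching early termination column or footnote to the schedule, so that a termination visit before Week 8 collects, besides the Week 9 items, the Week 8 safety assessments already in the protocol: labs, the limited physical examination, PHQ-8, C-SSRS (Since Last Visit version), local tolerability, and the urine pregnancy test where applicable. Keep the Week 9 list alone for exits after Week 8.

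BSA, WI-NRS, DLQI and Scalpdex at exit are optional, because their endpoints are tied to fixed weeks. Leave PK out: samples are defined as trough/pre-dose on Days 0, 28 and 56 (1.3, footnote h) and summarised as pre-dose concentrations (6.6). If an exit sample is taken anyway, record the time since the last application and keep it out of that summary.

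The cost is one sentence and a schedule entry. For each subject concerned it adds one blood and urine sample, a short examination and short questionnaires at a visit already planned, all of which the sites already perform. Off-schedule values also need a visit-assignment rule, which can go in the SAP. The change adds data collection only.

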5.6 Unscheduled Visit

Unscheduled visits may be necessary to repeat testing following abnormal laboratory results, for follow-up of AEs, or for any other reason, as warranted in the judgment of the Investigator.

5.7 Adverse Events

5.7.1 Adverse Event Definition

An AE means any untoward medical occurrence associated with the use of a drug in humans, whether or not considered drug related. An AE can therefore be any unfavorable and unintended sign (including an abnormal laboratory finding), symptom, or disease temporally associated with the use of a medicinal (investigational) product, whether or not related to the medicinal (investigational) product.

AEs will be collected following informed consent of the subject through subject study completion.

A treatment emergent adverse event (TEAE) is defined as an AE that started post application of IP at the Baseline visit through study completion.

Application site reactions will be considered adverse events if they require intervention, suspension or discontinuation of IP.

5.7.2 Serious Adverse Event

The definitions and reporting requirements of Health Canada/the Food and Drug Administration (FDA)/ICH Guidelines for Clinical Safety Data Management, Definitions and Standards for Expedited Reporting, Topic E2A will be adhered to. If any AEs are serious, as defined by ICH Guidelines for Clinical Safety, required procedures will be followed.

All SAEs will be reported to the Sponsor via fax or e-mail within 24 hours of becoming aware of the event, whether or not the SAEs are deemed drug-related. Refer to the Safety Reporting Instructions for details on how to submit the SAE Report. All serious event reporting will adhere to ICH E6: Guideline for Good Clinical Practice and ICH E2A: Clinical Safety Data

Management: Definitions and Standards for Expedited Reporting.: The ERB/IRB will be notified of the Alert Reports as per HC, FDA, ICH and the IRB/ERB's policies and procedures.

An SAE is any AE that in the view of either the PI or Sponsor, results in any of the following outcomes: Death, a life-threatening AE, inpatient hospitalization or prolongation of existing hospitalization, a persistent or significant incapacity or substantial disruption of the ability to conduct normal life functions, or a congenital anomaly/birth defect. Important medical events that may not result in death, be life-threatening, or require hospitalization may be considered serious when, based upon appropriate medical judgment, they may jeopardize the subject and may require medical or surgical intervention to prevent one of the outcomes listed in the above definition. Examples of such medical events include allergic bronchospasm requiring intensive treatment in an emergency room or at home, blood dyscrasias or convulsions that do not result in inpatient hospitalization, or the development of drug dependency or drug abuse.

Life-threatening is defined as an AE that in the view of the PI or Sponsor, places the subject at immediate risk of death. It does not include an AE that, had it occurred in a more severe form, might have caused death.

Hospitalization does not include the following:

- Rehabilitation facilities, hospice facilities or respite care (e.g. caregiver relief)
- Nursing homes or skilled nursing facilities
- Emergency room visits
- Same day surgeries (as outpatient/same day/ambulatory procedures)
- <24 hour admissions for observation or evaluation

Hospitalization or prolongation of hospitalization in the absence of a precipitating, clinical AE is not in itself an SAE. Examples include:

- Admission for treatment of a preexisting condition that did not worsen
- Hospitalizations for cosmetic elective surgery, social, and/or convenience admissions
- Pre-planned treatments or surgical procedures should be noted in the baseline documentation for the individual subject.
- Diagnostic and therapeutic procedures, such as surgery, should not be reported as AEs; however, the medical condition for which the procedure was performed should be reported if it occurs during the reporting period and meets the definition of an AE. For example, an acute appendicitis that begins during the AE reporting period should be reported as an AE, and the resulting appendectomy should be recorded as treatment of the AE.

Unexpected is defined as an AE that is not listed in the IB or is not listed at the specificity or severity that has been observed; or is not consistent with the risk information described in the general investigational plan or elsewhere in the current IND/CTA.

If a SAE occurs to a subject on this study, contact the Medical Monitor within one business day of knowledge of event.

5.7.3 Suspected Unexpected Serious Adverse Reaction (SUSAR)

This is defined as a serious adverse reaction, the nature or severity of which is not consistent with the known study treatment information. A serious event or reaction is not defined as a SUSAR when: 'it is serious but expected' or it does not fit the definition of an SAE, whether expected or not.

5.7.4 Safety Review

At each follow-up visit, subjects will be queried with an open-ended question such as: 'How have you been feeling since your last visit?' Additionally, the study staff will review subject diaries and, if it appears that a potential AE was recorded, study staff will query the subject and determine if an AE occurred.

AEs (whether serious or non-serious) and clinically significant abnormal laboratory test value(s) will be evaluated by the Investigator and treated and/or followed up for up to one month after end of treatment until the symptoms or value(s) return to normal, or acceptable levels, as judged by the Investigator.

Where appropriate, medical test(s) and/or examination(s) will be performed to document resolution of event(s). Outcome may be classified as resolved, improved, unchanged, worse, fatal or unknown (lost to follow-up).

